12.0 HUMAN SUBJECT PROTECTION AND ETHICAL OBLIGATIONS

12.1 Regulatory and Ethical Approval

The study will be conducted in accordance with all conditions of approval by the relevant regulatory authorities and ethics committee. In South Africa, this study will be conducted under the oversight of SAHPRA in accordance with ICH GCP guidelines. CAPRISA will be responsible for reporting study-related information to SAHPRA. The study will also be conducted under the oversight of the UKZN's BREC. In Zambia, the study will be conducted under the oversight of Zambia Medicines Regulatory Authority (ZAMRA) in accordance with ICH GCP guidelines. CIDRZ will be responsible for reporting study-related information to ZAMRA. The study will also be conducted under the oversight of the Zambia Biomedical Ethics Review Committee (UNZABREC)

12.2 Informed consent

Written informed consent will be obtained from each study participant in the language of their choice prior to screening and enrolment, in accordance with ICH GCP guidelines. Participants will be provided with copies of the informed consent forms if they are willing to receive them. A comprehension assessment will also be completed as per the SOE.

12.3 Risks and Benefits

Risks associated with the use of monoclonal antibodies

Administration of mAbs may have a risk of immune reactions such as acute anaphylaxis, serum sickness and the generation of antibodies. However, these reactions are rare and more often associated with mAbs targeted to human proteins or with the use of murine mAbs that would have a risk of human anti-mouse antibodies (33). In this regard, because the mAbs are targeted to a viral antigen and are human mAbs, they are expected to have a low risk of such side effects.

Typically, the side effects of mAbs are mild but may include fever, chills, rigors, nausea, vomiting, pain, headache, dizziness, shortness of breath, bronchospasm, hypotension, hypertension, pruritus, rash, urticaria, angioedema, diarrhoea, tachycardia or chest pain. These side effects typically occur within the first 24 hours and are generally due to the body's natural response to the receipt of the antibody. The receipt of antibodies may also cause redistribution of immune and blood cells. This may not have any clinical effect but will be observed as a transient blood laboratory abnormality (33, 34). Clinical use of mAbs that are targeted to cytokines or antigens associated with human cells may be associated with an increased risk of infection however this is not expected to be a risk for a mAb targeted to a viral antigen (44).

Human mAbs directed against the cell surface targets on lymphocytes may be associated with cytokine release, causing a reaction known as “cytokine release syndrome” (CRS). Most infusion-related events occur within the first 24 hours after beginning administration (45). Severe reactions, such as anaphylaxis, angioedema, bronchospasm, hypotension and hypoxia, are infrequent and more often associated with mAbs targeted to human proteins or with non-human mAb, such as a murine mAb (46). CRS reactions most commonly occur within the first few hours after beginning the infusion and with the first mAb infusion received. This is because the cytokine release is associated with lysis of the cells targeted by the mAb and the burden of target cells is greatest at the time of the first mAb treatment. With licensed therapeutic mAbs used intravenously, CRS is managed by temporarily stopping the infusion, administering histamine blockers and restarting the infusion at a slower rate. Delayed allergic reactions to a mAb may include a serum sickness type of reaction, which is characterized by urticaria, fever, lymph node enlargement, and joint pains. Symptoms may not appear until several days after the exposure to the mAb. This type of reaction is noted to be more common with chimeric types of mAb.

Risks of blood drawing

Blood drawing may cause pain and bruising and, infrequently, may cause a feeling of light-headedness or fainting. Rarely, it may cause infection at the site where blood is taken. Problems from blood drawing are generally mild and may include pain, bruising, minor swelling or bleeding at the injection site and rarely, infection, vein irritation (called phlebitis), or blood clot.

Risks associated with genital sample collection

Collection of samples by swabs, cytobrushes and/or SoftCup could entail slight discomfort.

Benefits

There are no direct benefits to participants from study participation. Others may benefit from knowledge gained in this study that may aid in the development of HIV prevention or therapeutic methods. Participants will receive HIV/STI risk reduction counselling, HIV and STI testing, physical examination, and routine laboratory testing. Participants will be provided STI treatment in accordance with WHO guidelines free of charge. For other medical conditions identified as part of the study screening and/or follow-up procedures, participants will be referred to other sources of care available in their community.

Compensation

Pending regulatory approval, participants will be compensated for time and effort in this study, and/or be reimbursed for travel to study visits and time away from work. Site-specific reimbursement amounts will be specified in the study informed consent forms. The study site will determine appropriate compensation with their overseeing regulatory boards.

Subject confidentiality

Every effort will be made to protect participant privacy and confidentiality to the extent permitted by law. Study-related information will be stored securely at the study research clinic. All participant information will be stored in lockable file cabinets in areas with access limited to study staff. Data collection, process, and administrative forms, laboratory specimens, and other reports will be identified by a coded number only, to maintain participant confidentiality. All records that contain names or other personal identifiers, such as locator forms and informed consent forms, will be stored separately from study records identified by code number. All databases will be secured with password-protected access systems. Forms, lists, logbooks, appointment books, and any other listings that link PID numbers to other identifying information will be stored in a separate, locked file in an area with limited access. Participants' study data, as identified by PID number only, will not be released without their written permission, except as necessary for review and monitoring by authorized regulatory and study representatives.

Study discontinuation

This study may be discontinued at any time if approval for the study is withdrawn by regulatory authorities and ethics committees. In addition, the DSMB may recommend that the Protocol Team discontinue the study for safety reasons at any time.

References

1. UNAIDS. WHO, HIV/AIDS Fact sheet: 2020 statistics. 2020; [https://www.who.int/news-room/fact-sheets/detail/hiv-aids].

Appendix 1. Part A: Group 1a/1c Schedule of Evaluations (4 monthly)

Product Administration Phase												Study Exit	
Study Month	SCR	M0			M2	M4			M6	M8		M10	M12
Study Week		W0				W16				W32			
Virtual Visit (1)			VV1	VV2			VV3	VV4			VV5	VV6	
Study Day (post study product/placebo)		D0	D3	D7		D0	D3	D7		D0	D3	D7	
Study Product/ Placebo administration		X				X				X			
Administrative, Behavioural and Regulatory Procedures													
Informed consent for study participation	X												
Comprehension assessment	X	X											
PID assignment	X												
Eligibility assessment (2)	X	X				X				X			
Locator information	X	X			X	X			X	X		X	X
Demographic information	X												
Randomisation		X											
Behavioural Assessment	X	X			X	X			X	X		X	X
Risk Reduction counselling	X	X			X	X			X	X		X	X
HIV-test Counselling (3)	X	X			X	X			X	X		X	X
Contraceptive counselling and provision (4)	X	X			X	X			X	X		X	X
Product acceptability assessment		X				X				X			
Clinical Procedures													
Comprehensive Medical History	X												
Interim Medical History		X	X	X	X	X	X	X	X	X	X	X	X
Concomitant Medications	X	X	X	X	X	X	X	X	X	X	X	X	X
Comprehensive Physical Exam	X												
Targeted Physical Exam		X			X	X			X	X		X	X
Weight	X	X			X	X			X	X		X	X
Height	X												
Vital Signs	X	X			X	X			X	X		X	X
Reactogenicity Assessment (5)		X	X	X		X	X	X		X	X	X	
Adverse Events		X	X	X	X	X	X	X	X	X	X	X	X
Clinical Laboratory Tests (6)													
Full Blood Count, differential	X	X				X				X			
ALT, creatinine	X	X				X				X			
Pregnancy test (7)	X	X			X	X			X	X		X	X
HIV testing (8)	X	X			X	X			X	X		X	X
Storage (6)													
Plasma Storage	X	X				X				X			X
Serum Storage	X	X				X				X			X
Pharmacokinetics sampling (9)	X	X			X	X			X	X		X	X
Genital mucosal sampling (10)		X				X							
PBMCs		X											X

1. Refers to any remote consult with a participant as described in the protocol and SSP.

2. Eligibility to enrol into the study will be assessed before the first study product administration and eligibility to receive study product will be assessed thereafter

3. Includes pre-test counseling and post-test counseling as indicated. A subsequent follow-up contact may be conducted to provide post-test counseling and to report results to participant.

4. Conducted when clinically indicated

5. Reactogenicity assessments performed at approximately 60 minutes post study product administration and via virtual visit three days post study product administration as per protocol. If required, this information will be updated on Day 7 virtual visit.

6. Total blood volume collection will not exceed 500 ml within 6 weeks

7. May include urine or serum pregnancy test as clinically indicated

8. HIV testing will be conducted as per an HIV testing algorithm described in the SSP

9. PK assessments will be conducted retrospectively on stored samples for all HIV seroconvertors and a sub-set of participants at a minimum of two timepoints

10. Genital mucosal sampling will include cytobrushes, genital swab/s and/or Softcup.

Appendix 2. Part A: Group 1b/1c Schedule of Evaluations (6 monthly)

Product Administration Phase										
Study Month	SCR	M0			M3	M6			M9	Study Exit
Study Week		W0				W24				M12
Virtual Visit (1)			VV1	VV2			VV3	VV4		
Study Day (post study product/placebo)		D0	D3	D7		D0	D3	D7		
Study Product/ Placebo administration		X				X				
Administrative, Behavioural and Regulatory Procedures										
Informed consent for study participation	X									
Comprehension assessment	X	X								
PID assignment	X									
Eligibility assessment (2)	X	X				X				
Locator information	X	X			X	X			X	X
Demographic information	X									
Randomisation		X								
Behavioural Assessment	X	X			X	X			X	X
Risk Reduction counselling	X	X			X	X			X	X
HIV-test Counselling (3)	X	X			X	X			X	X
Contraceptive counselling and provision (4)	X	X			X	X			X	X
Product acceptability assessment		X				X				
Clinical Procedures										
Comprehensive Medical History	X									
Interim Medical History		X	X	X	X	X	X	X	X	X
Concomitant Medications	X	X	X	X	X	X	X	X	X	X
Comprehensive Physical Exam	X									
Targeted Physical Exam		X			X	X			X	X
Weight	X	X			X	X			X	X
Height	X									
Vital Signs	X	X			X	X			X	X
Reactogenicity Assessment (5)		X	X	X	X	X	X	X	X	X
Adverse Events		X	X	X	X	X	X	X	X	X
Clinical Laboratory Tests (6)										
Full Blood Count, differential	X	X				X				
ALT, creatinine	X	X				X				
Pregnancy test (7)	X	X			X	X			X	X
HIV testing (8)	X	X			X	X			X	X
Storage (6)										
Plasma Storage	X	X				X				X
Serum Storage	X	X				X				X
Pharmacokinetics sampling (9)	X	X			X	X			X	X
Genital mucosal sampling (10)		X				X				X
PBMCs		X								X

1. Refers to any remote consult with a participant as described in the protocol and SSP.
2. Eligibility to enrol into the study will be assessed before the first study product administration and eligibility to receive study product will be assessed thereafter
3. Includes pre-test counseling and post-test counseling as indicated. A subsequent follow-up contact may be conducted to provide post-test counseling and to report results to participant.
4. Conducted when clinically indicated
5. Reactogenicity assessments performed at approximately 60 minutes post study product administration and via virtual visit three days post study product administration as per protocol. If required this information will be updated on the DAY 7 virtual visit.
6. Total blood volume collection will not exceed 500 mls within 6 weeks
7. May include urine or serum pregnancy test as clinically indicated
8. HIV testing will be conducted as per an HIV testing algorithm described in the SSP
9. PK assessments will be conducted retrospectively on stored samples for all HIV seroconvertors and a sub-set of participants at a minimum of two timepoints
10. Genital mucosal sampling will include cytobrushes, genital swab/s and/or Softcup.

Appendix 3. Part B: Schedule of Evaluations (6 monthly)

Product Administration Phase																			Study Exit #
Study Month	SCR	M0		M3	M6		M9	M12		M15	M18		M21	M24	M27	M30			
Study Week		W0			W24			W48			W72								
Virtual Visit (1)			VV1	VV2		VV3	VV4		VV5	VV6		VV7	VV8						
Study Day (post study product/placebo)		D0	D3	D7		D0	D3	D7		D0	D3	D7							
Study Product/ Placebo administration		X			X			X		X									
Initiative, Behavioural and Regulatory Procedures																			
Informed consent for study participation	X																		
Comprehension assessment	X	X																	
PID assignment	X																		
Eligibility assessment (2)	X	X			X			X		X									
Locator information	X	X			X	X		X	X		X	X		X	X	X			
Demographic information	X																		
Randomisation		X																	
Behavioural Assessment	X	X			X	X		X	X		X	X		X	X	X			
Risk Reduction counselling	X	X			X	X		X	X		X	X		X	X	X			
HIV-test Counselling (3)	X	X			X	X		X	X		X	X		X	X	X			
Contraceptive counselling and provision (4)	X	X			X	X		X	X		X	X		X	X	X			
Product acceptability assessment		X			X			X			X								
Clinical Procedures																			
Comprehensive Medical History	X																		
Interim Medical History		X	X	X	X	X	X	X	X	X	X	X	X	X	X	X			
Concomitant Medications	X	X	X	X	X	X	X	X	X	X	X	X	X	X	X	X			
Comprehensive Physical Exam	X																		
Targeted Physical Exam		X			X	X		X	X		X	X		X	X	X			
Weight	X	X			X	X		X	X		X	X		X	X	X			
Height	X																		
Vital Signs	X	X			X	X		X	X		X	X		X	X	X			
Reactogenicity Assessment (5)		X	X	X	X	X	X	X	X	X	X	X	X	X	X	X			
Adverse Events		X	X	X	X	X	X	X	X	X	X	X	X	X	X	X			
Clinical Laboratory Tests (6)																			
Full Blood Count, differential	X	X			X			X			X								
ALT, creatinine	X	X			X			X			X								
Pregnancy test (7)	X	X			X	X		X	X		X	X		X	X	X			
HIV testing (8)	X	X			X	X		X	X		X	X		X	X	X			
Storage (6)																			
Plasma Storage	X	X			X			X			X								
Serum Storage	X	X			X			X			X								
Pharmacokinetics sampling (9)	X	X			X	X		X	X		X	X		X	X	X			
Genital mucosal sampling (10)		X			X			X			X								
PBMCs		X														X			

- 1.Refers to any remote consult with a participant as described in the protocol and SSP.
- 2.Eligibility to enrol into the study will be assessed before the first study product administration and eligibility to receive study product will be assessed thereafter
- 3.Includes pre-test counseling and post-test counseling as indicated. A subsequent follow-up contact may be conducted to provide post-test counseling and to report results to participant.
4. Conducted when clinically indicated
- 5.Reactogenicity assessments performed at approximately 60 minutes post study product administration and via virtual visit three days post study product administration as per protocol. If required this information will be updated on the DAY 7 virtual visit.
- 6.Total blood volume collection will not exceed 500 mls within 6 weeks
- 7.May include urine or serum pregnancy test as clinically indicated
- 8.HIV testing will be conducted as per an HIV testing algorithm described in the SSP
- 9.PK assessments will be conducted retrospectively on stored samples for all HIV seroconvertors and a sub-set of participants at a minimum of two timepoints
- 10.Genital mucosal sampling will include ~~eyebushes~~, genital swab/s and/or Softcup.

#Once the last dose is received, participants will be followed up to the next 6 month point to exit the product part of the study and start the 6-month safety and PK follow-up off-product

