3.3 Secondary objectives

- To evaluate the tolerability of CAP256V2LS and VRC07-523LS
- To assess the PK profile of study products administered 16 weekly (4 monthly) in comparison to 24 weekly (6 monthly) administration
- To assess the PK profile of study products administered as a fixed dose 24 weekly (6 monthly)
- To compare HIV incidence rates in antibody and placebo recipients
- To assess CAP256V2LS and VRC07-523LS systemic and mucosal concentrations in

relation to breakthrough infections

- To determine the prevalence of autoantibody induction
- To assess participant acceptability of the subcutaneous injections

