3.5 Secondary endpoints

- Documented HIV-1 infection during follow up
- Differences in the PK profile of study products administered 16 weekly (4 monthly) in comparison to 24 weekly (6 monthly) administration
- Differences in the PK profile of study products administered as weight-based dosing in comparison to fixed dosing.
- Changes in the concentration of systemic and mucosal concentrations of CAP256V2LS and VRC07-523LS titres in breakthrough infections
- Proportion of participants reporting CAP256V2LS injections to be acceptable as per study questionnaire

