4.2 Enrollment plan

The study is divided into two parts: **Part A** and **Part B**.

In **Part A (N=90)**, participants will be randomised in a 2:1:2:1 ratio to receive the following: CAP256V2LS 20mg/kg and VRC07- 523LS 20mg/kg administered SC every 16 weeks (4 monthly) or placebo; CAP256V2LS and VRC07-523LS antibodies administered SC every 24 weeks (6 monthly) or placebo (**Table 2**) They will then be followed up and exit the study at Month 12.

In **Part B (N=900)**, participants will be randomised in a 1:1 ratio. Participants will receive an initial fixed dose of 1.2g of CAP256V2LS and 1.2g VRC07-523LS or placebo followed by 600mg of CAP256V2Ls and 1.2g of VRC07-523LS or placebo administered SC every 24 weeks (6 monthly) or placebo. Participants will be followed-up for approximately an average of 18 months with a maximum follow-up of 24 months. Once the last dose is received, participants will be followed up to the next 6 month point to exit the product part of the study and start the 6-month safety and PK follow-up off-product.

All inclusion and exclusion criteria must be met for eligibility to enrol. Enrolment will take place within 56 days of screening. The study accrual period is planned for approximately 10-12 months and eligible participants will receive between approximately 2 to 4 doses in Part B depending the length of time taken to accrue the full cohort.

Safety assessments will be conducted at baseline, following product administration, and at regular intervals as per the Schedule of Evaluations (SOE). PK assessments will be conducted retrospectively on stored samples for all HIV seroconvertors and a sub-set of participants at a minimum of two timepoints. HIV testing will be conducted as per the SOE.

Table 2: CAPRISA 012C dosing table

Part A

Group	Participants	Regimen*	N= 90	Dose (mg/kg)
1a	HIV negative	CAP256V2LS + VRC07-523LS	30	20 mg/kg SC + 20 mg/kg SC at 16-week (4 monthly) dosing intervals
1b	HIV negative	CAP256V2LS + VRC07-523LS	30	20 mg/kg SC + 20 mg/kg SC at 24-week (6 monthly) dosing intervals
1c	HIV negative	Placebo	30 (15 each)	Normal saline SC at 16 or 24-week (4 or 6 monthly) dosing intervals

*Study products will be administered as two separate injections with or without hyaluronidase.

Part B

Group	Participants	Regimen*	N=900	Dose (mg/kg)

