5.10 Follow-up visits

All follow up visits will take place as per the SOE. For all participants, reactogenicity assessments are performed before (baseline) and after each study product administration as per the SSP. A reactogenicity assessment will be conducted at the clinical site on Day 0, approximately 60 minutes post study product administration. In addition, all participants will be asked to keep a daily diary of local and systemic symptoms for 3 days after each product administration. All participants will be counselled on the expected reactogenicity events and on how to record these events. Participants will also be asked to record their temperature daily from Day 0 to Day 3.

A virtual visit will be conducted by study staff on Day 3 and Day 7 post study product administration or sooner if indicated. In this protocol, a virtual visit refers to any remote or web-based consult with a participant and includes but is not limited to telephonic communication, email communication, messaging, video calls or web applications. At these virtual visits, study staff will discuss reactogenicity events and/or adverse events with the participant and record the relevant information on either the appropriate CRF(s) or participant chart note as per SSP. Clinic staff will follow new or unresolved reactogenicity symptoms present at day 3 to resolution. In general, a participant who self-reports any event greater than moderate and/or requires medical intervention is seen by a clinician within 48 hours after onset, unless the reaction is improving and/or has completely resolved.

All laboratory tests will take place as per the SOE. The total blood volume drawn from each participant will comply with regulatory guidelines. Additional assessments of health and/or laboratory tests may be conducted at follow up visits based on clinical judgement. Laboratory test(s) may be repeated at the discretion of the PI or designee.

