8.4 Discontinuation of study product/s administration

Participants will be withdrawn from study product use for any of the reasons listed below. These participants will not receive any additional dose of study product but will continue safety follow-up as per SSP.

- Pregnancy
- Immediate hypersensitivity reaction associated with the study product
- Any grade 4 reactogenicity event that is assessed as related to the study product
- Any grade 3 or higher adverse event that is assessed as related to the study product
- An SAE that is subsequently considered to be related to study product
- Intercurrent illness that is not expected to resolve prior to the next scheduled study product administration, which is assessed by the PI (or designee) to require withdrawal from the product administration
- Repeated failure to comply with protocol requirements
- Co-enrolment into another study that in the opinion of the PI may interfere with the study objectives and participant safety
- The study PI decides to stop or cancel the study.
- The regulatory authorities halt the study.

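### Acceptability is scheduled only at dosing visits, so the last planned dose and any dose that ends product use may have no rating after the reaction period

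*Protocol*

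**What the plan says.** Protocol section 3.3 lists as a secondary objective "To assess participant acceptability of the subcutaneous injections". Section 3.5 gives it an endpoint: "Proportion of participants reporting CAP256V2LS injections to be acceptable as per study questionnaire". The endpoint names neither the visit that counts nor the denominator.

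The timing is fixed in the appendices, in the row "Product acceptability assessment". Appendix 1 marks M0, M4 and M8. Appendix 2 marks M0 and M6. Appendix 3 shows four marks. Its columns are broken in the text at hand, but the pattern equals that of the full blood count and ALT/creatinine rows and fits the dosing visits M0, M6, M12 and M18.

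For reactions, section 5.10 asks women to "keep a daily diary of local and systemic symptoms for 3 days after each product administration". In section 8.4, women withdrawn from product "will not receive any additional dose of study product but will continue safety follow-up as per SSP". In Part B, section 4.2 says that "eligible participants will receive between approximately 2 to 4 doses in Part B", and then: "Once the last dose is received, participants will be followed up to the next 6 month point". Under its acceptability heading, section 9.4.2 reports product discontinuations and study withdrawals by arm, with reasons. It does not mention the questionnaire.

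**The concern.** A dosing-day answer about that day's injection is given either before the injection or within hours of it. The protocol does not say which. In both cases most of the 3-day reaction period lies ahead. The first scheduled chance to judge the whole experience is the next dosing visit, 16 or 24 weeks later. After the last planned dose there may be no such chance, and a woman who stops product has no further dosing visit.

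Some reasons for stopping in section 8.4 are bad experiences with the product: immediate hypersensitivity, a related grade 4 reactogenicity event, or a related grade 3 or higher adverse event. Missing post-reaction answers may therefore be concentrated in women with reason to find the injections unacceptable. At stake is whether the endpoint describes all women who were injected, or mainly those who came back for another dose. No analysis can recover answers that were never collected, so this has to be settled in the schedule.

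**Working it through.** The protocol states no acceptability rate, precision or sample size for this endpoint, so there is no figure to reproduce. The check compares the schedules and then asks what the protocol allows one to say about bias.

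**1. Doses with a later scheduled rating.** With k doses and a questionnaire only on dosing days, a dose is rated after its reaction period only at the following dosing visit. That gives k − 1 doses with a later scheduled rating and 1 without.

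| Group | Doses (k) | Later rating scheduled | No later rating |
|---|---|---|---|
| Part A, 4-monthly | 3 | 2 | 1 of 3 |
| Part A, 6-monthly | 2 | 1 | 1 of 2 |
| Part B, four doses | 4 | 3 | 1 of 4 |
| Part B, two or three doses | 2 or 3 | 1 or 2, or all | unclear |

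The last row is unclear for this reason. A woman with two doses (M0, M6) is followed to M12, and one with three (M0, M6, M12) to M18. Both months appear to carry the mark because they are dosing visits for others. Whether the questionnaire is given there without a dose is not stated. After four doses the next 6-month point is M24, which has no mark.

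**2. Women who stop product.** Section 5.3 defines enrolment as receipt of the dose, so every enrolled woman has an M0 questionnaire scheduled. A woman withdrawn after her first dose has that answer, given on the day of injection. No schedule marks a questionnaire at product stop, and section 8.4 leaves her later follow-up to the study-specific procedures.

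**3. Possible bias.** Let d be the share of dosed women who stop, p_stay the acceptance among those who continue, and p_stop the acceptance among those who stop, judged after their reactions.

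- If stoppers are left out, the reported proportion is p_stay and the proportion over all dosed women is (1 − d)·p_stay + d·p_stop. The bias is d·(p_stay − p_stop).
- If stoppers are kept with their same-day answer, at rate p_same, the bias is d·(p_same − p_stop).

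Each expression is positive only if p_stop is the lower term. It is zero if the two rates are equal and negative if p_stop is higher. The protocol gives none of these quantities. The 10% in section 9.2 (Part B) is a dropout allowance explained by the interval between visits. It is not a rate of stopping product and cannot stand in for d.

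**4. Room in the schedule.** The behavioural assessment row is marked at the mid-interval and exit visits in Appendices 1 and 2, and at visits beyond the dosing days in Appendix 3. Questionnaire work is already done at such visits.

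**The case against.** The strongest reply is that nobody is shown to leave the proportion. Every enrolled woman has the M0 questionnaire, the endpoint counts participants rather than injections, and its visit and denominator are details a protocol may leave to the analysis plan. A woman who answers at her second dosing visit has already lived through one full reaction period. Reactions are also recorded separately, by the 60-minute assessment, the diary and the Day 3 and Day 7 contacts, and tolerability is its own objective. Section 9.4.2 makes discontinuations visible by arm, with reasons.

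Much of this stands, and it limits the point. A reader might infer that stoppers drop out of the proportion, but section 3.5 fixes no denominator that would exclude them. A reader might also infer that no woman ever rates her last injection, but that is unsettled for Part B women with two or three doses. Pregnancy, intercurrent illness and co-enrolment are also reasons to stop and need not reflect dislike of the injections.

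What does not stand is that the other records fill the gap. Diaries and discontinuation counts show what happened, not whether the woman found the injections acceptable, and the counts mix reasons unrelated to the injections. An analysis plan can choose among collected answers but cannot add one after the reaction that ended dosing.

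**Conclusion.** The point holds as a limited weakness of design. No acceptability rating is scheduled after the reaction period of the last planned dose in Part A or for Part B women with four doses, and none is tied to stopping product in any group. This rests on reading the four Part B marks as the dosing visits, which the matching laboratory rows support.

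The acceptability proportion could be biased upward. It is tempting to say that it is inflated, or to attach a range, but the documents do not support either: that would need acceptance rates and a product-stop rate that the protocol does not give. The discontinuation counts by arm offset the weakness only in part. The endpoint is secondary, and nothing here touches the primary safety comparison, so this is an inexpensive improvement rather than a serious fault.

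**What to change.** Keep the dosing-day marks and add the questionnaire at contacts already scheduled:

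- the first clinic visit after each dose: M2, M6 and M10 in Appendix 1; M3 and M9 in Appendix 2; M3, M9, M15 and M21 in Appendix 3;
- the exit visit in all three;
- the first scheduled visit after product is stopped for any reason.

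State in section 3.5 that the proportion is taken over all dosed women, using each woman's last available post-injection answer. The first two additions also settle the unclear case of Part B women with two or three doses.

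The cost is a few more minutes of questionnaire time at the affected visits, extra marks and a note in each appendix, and one sentence on the endpoint. No new visit, staff or clinical rule is needed. The change does not recover women who leave the study altogether, so the discontinuation table in section 9.4.2 should stay beside the result.
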